## **2.2 Analysis sets**

The safety set will be used for statistical analysis and data reporting.

The Safety Set includes all patients who received at least one dose of study drug after enrolling into the roll-over protocol.

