## **2 Statistical methods**

### **2.1 Data analysis general information**

Data will be analyzed by Novartis using SAS Version 9.3. Only data reported in the database of this protocol will be included in the analyses. Patient data from the parent study will not be taken into account.

Summary tables will be provided for patient disposition, demographic data and treatment exposure. All data collected on the database will be listed, using all patients enrolled in this study.

Categorical data will be presented as frequencies and percentages. For continuous data, mean, standard deviation, median, minimum, and maximum will be presented, unless otherwise stated.

The original protocol was released on 07-Dec-2012. Protocol amendment 1 (PA1) was released on 18-Mar-2016. In this amendment the primary endpoint was changed to safety to better characterize the long-term safety of the compound. In addition, the protocol has been amended to include the collection of all AEs (including non-serious AEs) and an investigator attestation of continued clinical benefit. Additional eCRFs were added to collect data related to

- Investigator attestation of clinical benefit at every quarterly visit
- All adverse events (based on original protocol only SAEs were collected and all SAEs were only collected in ARGUS safety database)
- Relevant medical history/current medical conditions
- Monthly at home pregnancy testing for female patients of child bearing potential (serum/urine)
- Study evaluation completion at the end of the 30 day safety follow up
- Related imaging, drug use 6 months prior to liver event, pathology, medical history possibly contributing to liver dysfunction, local laboratory results (viral serology, autoimmune, immunoglobulin, liver function tests), overview, potential impact of alcohol use, acetaminophen/paracetamol pertaining to liver event (only when drug-induced liver injury (DILI) cases occur)

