However, at the time of global protocol amendment was released, 32 out of 34 patients were enrolled; 21 patients ongoing; 11 patients had already discontinued the study. Only 2 patients consented after PA1 approval. Therefore, 32/34 patients did not have AEs collected in eCRFs before PA1, ~30% of enrolled patients had AEs reported in RDC clinical database after PA1, and ~50% of SAEs occurred before PA1 were not reported in RDC. Due to this, safety data from both ARGUS safety database and RDC clinical database will be analyzed separately for comprehensive and transparent safety data reporting in final CSR. See section 2.8.2 in detail.

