### **Analysis set and grouping for the analyses:**

The overall observation period will be divided into two mutually exclusive segments:

1. on-treatment period: from day of first dose of study medication in the roll-over study to 30 days after last dose of study medication

2. post-treatment period: starting at day 30+1 after last dose of study medication.

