### 2.8.2 Adverse events (AEs)

Verbatim terms will be coded to lower-level terms in the Medical Dictionary for Regulatory Activities (MedDRA). AEs will be coded to MedDRA. An assessment of severity grade will be made using NCI-CTCAE v4.03. Summary tables for adverse events (AEs) will include only AEs that started or worsened during the on-treatment period, the *treatment-emergent* AEs. The incidence of treatment-emergent adverse events (new or worsening from baseline) will be summarized by System Organ Class (SOC) and or Preferred Term (PT), severity (CTC Grade 1-4, 5 Death is excluded), type of adverse event, relation to study treatment.

Since safety data collection was changed in the protocol amendment released on 18-Mar-2016, CTC grade were captured in the RDC clinical database only after the protocol amendment. All SAEs including AESIs reported as SAEs were captured in ARGUS safety database throughout the study.

Thorough manual review was implemented to ensure SAEs reported both in ARGUS and RDC databases were uniquely matched without any missing or overlapped inputs.

Hence, AEs/SAEs from both ARGUS safety database and RDC clinical database will be summarized separately to ensure comprehensive and transparent safety data reporting. Global protocol amendment date (18-Mar-2016) as a general cutoff date will be applied to analyze safety data from RDC clinical database.

The following AE summary tables will be provided:

I. from Safety Database (ARGUS):

- All SAEs throughout the study
  - SAEs regardless of study treatment relationship by primary system organ class and preferred term
  - SAEs suspected to be study treatment relationship by primary system organ class and preferred term

- All AESI reported as SAEs as per protocol throughout the study
  - Serious AESIs regardless of study treatment relationship by safety topic and preferred term

II. from Clinical Database (RDC):

- AEs (non-serious AE and AESI) after protocol amendment
  - AEs regardless of study treatment relationship
    - a. by primary system organ class, preferred term and maximum CTC grade
    - b. by primary system organ class and preferred term
  - AEs suspected to be study treatment related
    - a. by primary system organ class, preferred term and maximum CTC grade
    - b. by primary system organ class and preferred term
  - AEs leading to study drug discontinuation regardless of study drug relationship by primary system organ class and preferred term

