  - AEs resulting in dose adjustment or interruption regardless of study drug relationship by primary system organ class and preferred term
  - AEs requiring additional therapy and concomitant medication regardless of study drug relationship by primary system organ class and preferred term
  - AESIs regardless of study treatment relationship
    - c. by primary system organ class, preferred term and maximum CTC grade
    - d. by primary system organ class and preferred term
  - AESIs suspected to be study treatment related
    - c. by primary system organ class, preferred term and maximum CTC grade
    - d. by primary system organ class and preferred term
  - AESIs leading to study drug discontinuation regardless of study drug relationship by primary system organ class and preferred term
  - AESIs resulting in dose adjustment or interruption regardless of study drug relationship by primary system organ class and preferred term
  - AESIs requiring additional therapy and concomitant medication regardless of study drug relationship by primary system organ class and preferred term
- SAEs after protocol amendment
  - SAEs regardless of study treatment relationship by primary system organ class and preferred term
  - SAEs suspected to be study treatment relationship by primary system organ class and preferred term

For legal requirements of ClinicalTrials.gov and EudraCT, two required tables on treatment-emergent non-serious AEs with an incidence greater than 5% in clinical database, and on-treatment deaths and treatment-emergent SAEs in ARGUS safety database will be provided by

system organ class and preferred term using the safety set. The rule for the calculation of the number of occurrences is detailed in the Appendix section 5.2.

All of these tables will display the number and percent of patients that experience the given event and will display events by MedDRA. Events will be displayed alphabetically for SOC and PT. All safety data (including those from the post-treatment periods) will be listed and those collected during the post-treatment period are to be flagged. The following listings will also be generated:

- Listing of AEs leading to study drug discontinuation
- Listing of AEs leading to dose adjustment or interruption
- Listing of SAEs in ARGUS safety database
- Listing of SAEs in RDC clinical database

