For each specified AESI, the number and percentage of patients with at least one event of the AESI occurring during the on-treatment period will be summarized. Summaries of these AESIs will be provided grouped by CTCAE grades, relationship, leading to treatment discontinuation, resulting in dose adjustment/interruption, etc.

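### The post-amendment RDC adverse event tables use the whole Safety Set as denominator, so patients who left before collection began count as event-free and each percentage is about 32% too low

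*SAP*

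**What the plan says.** **Analysis set.** SAP 2.2 states "The safety set will be used for statistical analysis and data reporting" and defines that set as everyone dosed in the roll-over study, whatever the date. Protocol 10.1 likewise defines only the Safety Set. Neither document gives another denominator.

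**Collection history.** SAP 2.1 says of AE data before the amendment: "based on original protocol only SAEs were collected and all SAEs were only collected in ARGUS safety database". It also reports that 32 of 34 patients were enrolled when the amendment was released and 21 of them were ongoing, and adds: "11 patients had already discontinued the study. Only 2 patients consented after PA1 approval".

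**RDC tables.** SAP 2.8.2 sets the period: "Global protocol amendment date (18-Mar-2016) as a general cutoff date will be applied to analyze safety data from RDC clinical database". It heads both the AE/AESI block and the SAE block from RDC as post-amendment. On content it says: "All of these tables will display the number and percent of patients that experience the given event". The registry tables, including non-serious AEs from the clinical database, are to be produced by "system organ class and preferred term using the safety set".

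**Period described for AESIs.** SAP 2.8.2.1 says that "the number and percentage of patients with at least one event of the AESI occurring during the on-treatment period will be summarized". SAP 2.8 defines that period as follows: "on-treatment period: from day of first dose of study medication in the roll-over study to 30 days after last dose of study medication".

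**Missing data.** SAP 2.5.3 marks the handling of missing values, censoring and discontinuations for the primary objective as not applicable.

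**The concern.** The numerator of each RDC percentage is restricted by date and the denominator is not. A patient who left before 18-Mar-2016 cannot enter the numerator, apart from someone still inside the 30-day window after last dose. That patient nevertheless stays in the denominator, so uncollected data are read as no event.

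The AESI wording adds to this. It presents the percentages as covering a period that begins at the first roll-over dose, while RDC collection began later for the 32 patients enrolled before the amendment.

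Frequency and severity of AEs/SAEs is the primary endpoint. SAP 2.8.2 says CTC grade was captured only in RDC and only after the amendment, and all-AE collection also began there. The severity and non-serious parts of the primary endpoint therefore rest on these tables. The study is descriptive, so the percentages are themselves the result. The registry non-serious AE table would carry the same dilution, and the SAP requires no explanation alongside it.

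**Working it through.** **Inputs (SAP 2.1)**
- Enrolled at release of the amendment: 32, of whom 21 were ongoing and 11 had discontinued.
- Consented afterwards: 2.
- Total enrolled: 34.

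**Reproducing the SAP's counts**
- 21 + 11 = 32
- 32 + 2 = 34

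**Patients who could contribute to a post-amendment RDC table**
- 21 + 2 = 23

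**Effect on a percentage.** For n patients with an event, the plan gives n/34, while the proportion among observable patients is n/23. The relative understatement does not depend on n:

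1 − (n/34)/(n/23) = 1 − 23/34 = 11/34 = 32.4%

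| Patients with event | Denominator 34 | Denominator 23 |
|---|---|---|
| 1 | 2.9% | 4.3% |
| 2 | 5.9% | 8.7% |
| 5 | 14.7% | 21.7% |
| 10 | 29.4% | 43.5% |

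The last row is close to the SAP's own statement that about 30% of enrolled patients had AEs in RDC after the amendment (0.30 × 34 = 10.2).

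**Sensitivity.** The SAP states neither the Safety Set size nor the number actually under RDC collection. The alternatives below are assumptions.

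| Assumption | Calculation | Understatement |
|---|---|---|
| 1 or 2 of the 11 never dosed | 1 − 23/33; 1 − 23/32 | 30.3%; 28.1% |
| 1 or 2 of the 23 never dosed | 1 − 22/33; 1 − 21/32 | 33.3%; 34.4% |
| 1 or 2 of the 11 within 30 days of last dose at the cutoff | 1 − 24/34; 1 − 25/34 | 29.4%; 26.5% |
| Only 22, 21 or 20 under collection | 1 − 22/34; 1 − 21/34; 1 − 20/34 | 35.3%; 38.2%; 41.2% |

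The last row is plausible because the amendment section of the protocol requires IRB/IEC approval before implementation. RDC collection may therefore have started after 18-Mar-2016 at some sites.

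**Registry threshold.** The rule of incidence above 5% needs two patients with either denominator: 1/34 = 2.9% and 1/23 = 4.3% fall below it, and 2/34 = 5.9% and 2/23 = 8.7% exceed it. With these denominators the listed terms do not change; their percentages do.

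**The case against.** The SAP's authors knew of the gap. The SAP was updated in June 2020 because of it. It gives the counts in 2.1, separates ARGUS from RDC, heads the RDC blocks as post-amendment, and adds a patient-level table and plot of collection time against treatment time in 2.8.1. Counts appear beside percentages, so a reader of the full report could recompute them. The study is single-arm with no hypothesis test. A common factor leaves the ranking of events and the split by grade unchanged. Outside the registry tables the denominator is inferred, because no table shells are available.

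Some of this stands:
- The Safety Set is named outright only for the registry tables. Elsewhere it follows from being the only set defined, and no text supports another reading.
- The 11 patients were unobserved for RDC data only. Their SAEs were collected in ARGUS throughout.
- SAP 2.1 is not consistent about SAEs. It says that pre-amendment SAEs went only to ARGUS, and also that about 50% of them were not reported in RDC, which implies that the rest were. The 18-Mar-2016 cutoff removes those from the RDC tables, so the point is unaffected.
- The 32% measures the gap to the post-amendment proportion in observable patients. It does not measure the whole bias in long-term AE frequency, because the 21 ongoing patients also lack non-serious AEs from before the amendment.

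Disclosure and a plot do not change any percentage, and the plot does not travel with the registry entry.

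**Conclusion.** The concern holds. Following the SAP as written dilutes every post-amendment RDC percentage, including the non-serious and graded parts of the primary endpoint. With all 34 enrolled patients dosed and 23 observable, the relative understatement is 32%. Under the alternatives considered it lies between 26% and 41%, and in none of them does it vanish. ARGUS SAE and serious AESI tables cover the whole study and are not affected. No hypothesis test depends on this, so it is a point that should be fixed and not one that undermines the study.

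**What to change.** 1. In SAP 2.2, add an RDC AE-evaluable set: Safety Set patients whose on-treatment period (to last dose + 30 days) includes at least one day on or after the start of RDC AE collection. Use the patient-level collection start behind the SAP 2.8.1 table where it exists, and 18-Mar-2016 otherwise. The patient-level date is preferable because a patient who left between release and local approval would otherwise count as evaluable.
2. Use this set as denominator for all RDC AE, AESI and SAE tables and for the registry non-serious AE table. Carry the post-amendment label into the table titles and the AESI text of 2.8.2.1. Keep the full Safety Set for ARGUS tables.
3. In SAP 2.5.3, state that non-serious AEs before the amendment were not collected and are not to be read as absent.
4. Record the added set in SAP 4, which now reports no change from the protocol.
5. Optionally, add events per 100 patient-years of collection time. The new denominator does not address the unobserved earlier time of the 21 ongoing patients.

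The cost is SAP wording and one derived flag, based on dose dates already defined in SAP 2.1.1. No new data are needed. The drawbacks are that the reported RDC percentages rise and the report must explain two denominators.

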## **2.3 Patient disposition, demographics and other baseline characteristics**

### **2.3.1 Patient disposition**

The number of patients ongoing, completed and discontinued from the treatment at the time of analysis as well as the primary reason for end of treatment will be summarized.

### **2.3.2 Patient demographics and other baseline characteristics**

For patients that are eligible to participate in this roll-over study, demographic data, like gender, age, previous study, site/center and subject number, and relevant medical history will be summarized descriptively.

### **2.3.3 Protocol deviation**

Protocol deviation data will be summarized.

## **2.4 Treatments (study treatment, rescue medication, concomitant therapies, compliance)**

### **2.4.1 Study treatment/compliance**

Exposure to everolimus and sandostatin LAR will be summarized for all treated patients and will be based only on dose administered within this protocol. Study treatment administered during the parent study will not be taken into account.

The following algorithm will be used to calculate the duration of exposure in days:

- Duration of exposure to everolimus (days) = (date of last administration of everolimus) – (date of first administration of everolimus) + 1.
- Duration of exposure to sandostatin LAR (days) = (date of last administration of sandostatin LAR + 27 days) – (date of first administration of sandostatin LAR) + 1.
- Duration of exposure to everolimus + sandostatin LAR (days) = max(date of last administration of everolimus, date of last administration of sandostatin LAR + 27 days) – min(date of first administration of everolimus, date of first administration of sandostatin LAR) + 1.

The date of first administration of everolimus is derived as the first date when a nonzero dose of everolimus was administered and recorded on the database of this protocol. The date of last administration of everolimus is defined as is the last date when a nonzero dose of study drug was administered and recorded on the database of this protocol. The date of first and last administration of sandostatin LAR is defined in the same way.

The duration of exposure in years is calculated by dividing the duration of exposure in days by 365.25. The duration includes the periods of temporary interruption.

- Duration of exposure in years for everolimus = (Last dosing date – First dosing date + 1)/365.25
- Duration of exposure in years for sandostatin LAR = (Last dosing date + 27– First dosing date + 1)/365.25
- Duration of exposure in years for everolimus + sandostatin LAR (days) = [max(date of last administration of everolimus, date of last administration of sandostatin LAR + 27 days) – min(date of first administration of everolimus, date of first administration of sandostatin LAR) + 1] /365.25.

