### 6.6.3.3 Handling of other study treatment

If the patient was receiving a combination therapy with an approved, commercially available treatment with everolimus in the parent protocol, and is eligible for the roll-over study, this combination therapy will be allowed until the patient permanently discontinues everolimus. All Sandostatin LAR® Depot dosages prescribed to the patient and all dose changes during the study must be recorded on the Sandostatin Dosage Administration Record eCRF.

Dispensation, compliance and accountability of any combination therapy administered to the patient is under the supervision and discretion of the investigator. Sandostatin LAR® Depot will be provided by Novartis or by the investigational site considering local regulations. Sandostatin LAR® Depot will be distributed in country-specific approved packaging.

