### **7.1.6 Follow up for safety evaluations**

All patients must be followed up for safety evaluations for 30 days after the last dose of everolimus. At the end of this period, the investigator should contact the patient to inquire about any adverse events or serious adverse events observed during this period. This could be done via a phone contact. Following this there are **no** further follow-up study visits.

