### **1.1 Study design**

[figure not shown]
This is a multi-center, open label study to better characterize the long-term safety of everolimus in patients currently being treated in a Novartis-sponsored Oncology Global Development and Global Medical Affairs (OGD&GMA) study and who are not progressing on the current study treatment as judged by the investigator.

Parent studies eligible to participate in the roll-over study will be decided by Novartis. Investigator initiated trials (IIT) will not be included. The primary objective of the parent study must have been reached and the parent study must be in the process of being completed and reported. Patients may be allowed to continue combination therapy with Sandostatin LAR® Depot if they are currently receiving this combination therapy on the parent protocol and at the discretion of the investigator.

Patients will continue to be treated in the roll-over protocol until they are no longer benefiting from their everolimus treatment as judged by the investigator (disease progression), they develop unacceptable toxicities, they withdraw consent, they are non-compliant to the protocol, the investigator feels it is no longer in the patient's best interest to continue everolimus therapy or the patient dies, whichever comes first. At every quarterly visit, the investigator is required to confirm that the patient continues to have clinical benefit and may continue receiving study treatment. A patient will reach the end of study when everolimus treatment is permanently discontinued.

The study is expected to remain open until such time that enrolled patients no longer need treatment with everolimus or are able to obtain commercial supply according to local regulations for their medical condition.

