### 2.8.1 Exposure to study treatment

Exposure will be assessed for both Everolimus and Everolimus + Sandostatin LAR.

The following analyses will be performed to assess study treatment exposure:

- Duration of study drug exposure in years;
- Cumulative dose;
- Actual dose intensity;
- Dose adjustments and discontinuation;

Separate table and plot for on-treatment period and AEs/SAEs collection period in clinical database on patient level will be generated to reflect the proportion of safety data collection within the overall treatment period.

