### **2.8.3 Deaths**

CTC Grade 5 will not be used in this study; rather, information about deaths will be collected on the CRF End of Treatment (EOT) page. Deaths reportable as SAEs will be listed by patient and tabulated by type of adverse event.

All deaths will be summarized. Following summaries will be provided:

- On-treatment death in RDC clinical database by primary system organ class and preferred term
- All deaths in ARGUS safety database by system organ class and preferred term

Listing of all deaths in ARGUS safety database will also be provided.

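### Sandostatin LAR and combination exposure run 27 days past the last injection with no stop at death, so some days after death can count as exposure

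*SAP*

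**What the plan says.** SAP 2.4.1 defines Sandostatin LAR exposure in days as "Duration of exposure to sandostatin LAR (days) = (date of last administration of sandostatin LAR + 27 days" and then subtracts the first injection date and adds one. Combination exposure ends at "max(date of last administration of everolimus, date of last administration of sandostatin LAR + 27 days", with the earlier of the two first-dose dates as its start. Both are repeated in years by dividing by 365.25, so the 27-day extension appears four times. The last administration date is the last recorded nonzero dose (SAP 2.1.1 and 2.4.1). Everolimus alone has no extension.

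SAP 2.8.1 uses these durations: "Exposure will be assessed for both Everolimus and Everolimus + Sandostatin LAR". It adds no truncation rule, and no other section of the SAP or protocol caps exposure at death.

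Death on treatment is foreseen. SAP 1.1 ends treatment on a list of events that closes with "to continue everolimus therapy or the patient dies, whichever comes first", and SAP 2.8.3 plans a table of "On-treatment death in RDC clinical database by primary system organ class and preferred term".

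**The concern.** Adding 27 days after the last injection gives each injection 28 days of cover, which is reasonable for a depot that can be given monthly (protocol 2.1). That reasoning assumes the patient is alive for those days. If the patient dies within them, the formula places the end of exposure after the date of death.

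Long-term safety is the primary objective, and exposure duration is the context in which the adverse event counts are read. For an affected patient the report would contain a derived exposure end later than a death it also records. The stake is the accuracy of the Sandostatin LAR and combination duration summaries. SAP 2.8.1 also lists dose intensity but gives no formula, so it cannot be said whether that figure uses these durations.

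**Working it through.** The plan states no exposure figure to reproduce, so the check is date arithmetic on the SAP 2.4.1 formulas.

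**Inputs.** F = first injection, L = last injection, E = last everolimus dose, D = death = L + d. The value of d is not in the documents and is varied. The day of death is counted as exposed.

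**Sandostatin LAR alone.**
- SAP duration: (L + 27) - F + 1
- Capped duration: min(L + 27, D) - F + 1
- Excess: (L + 27) - min(L + 27, L + d) = max(0, 27 - d)

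**Combination.**
- Excess: max(E, L + 27) - max(E, min(L + 27, D))
- If d < 27, then E ≤ D < L + 27, because no dose follows death. The first maximum is L + 27 and the second is D, so the excess is again 27 - d.
- If d ≥ 27, the excess is 0.

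| d (days from last injection to death) | Overcount (days) |
|---|---|
| 0 | 27 |
| 7 | 20 |
| 14 | 13 |
| 21 | 6 |
| 26 | 1 |
| 27 or more | 0 |

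If d is assumed uniform over 0 to 26, the mean overcount is 378/27 = 14.0 days.

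**Example.** Both drugs start on day 1, the last injection is on day 337, everolimus is taken daily, and death is on day 344, so d = 7.
- SAP, Sandostatin LAR: 337 + 27 - 1 + 1 = 364 days
- SAP, combination: max(344, 364) - 1 + 1 = 364 days
- Capped, both: 344 days
- Overcount: 20 days, and 20/344 = 5.8%

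Had the last injection been on day 309 (d = 35), nothing would change.

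**Relative size per affected patient**, for assumed true exposures:

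| True exposure | Largest (27 days) | Mean (14 days) |
|---|---|---|
| 1 year (365.25 days) | 7.4% | 3.8% |
| 2 years (730.5 days) | 3.7% | 1.9% |
| 5 years (1826.25 days) | 1.5% | 0.8% |
| 10 years (3652.5 days) | 0.7% | 0.4% |

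**Effect on the group mean.** One affected patient among n combination patients raises the mean by at most 27/n days, or 14/n on average. The number n is not given; SAP 2.1 reports 34 enrolled, which is an upper bound. The smaller values are assumptions.

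| n | 27/n (days) | 14/n (days) |
|---|---|---|
| 5 | 5.4 | 2.8 |
| 10 | 2.7 | 1.4 |
| 20 | 1.4 | 0.7 |
| 34 | 0.8 | 0.4 |

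The reported maximum changes only if an affected patient has the longest duration, or reaches it through the extension.

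**Final data cut.** This does not raise the same problem. Protocol 6.6.3.3 says "this combination therapy will be allowed until the patient permanently discontinues everolimus", and protocol 7.1.6 says "All patients must be followed up for safety evaluations for 30 days after the last dose of everolimus". With L no later than E, the extension ends by E + 27, inside the 30-day follow-up, and the database is locked at the conclusion of the study (protocol 9.4).

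**The case against.** The strongest reply is that this changes no conclusion. No hypothesis is tested (SAP 2.5.2), adverse event tables give numbers and percentages of patients, and no exposure-adjusted rate is planned. The on-treatment window runs "to 30 days after last dose of study medication" and does not use these durations. All of that stands, and it is why the point is minor.

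A second reply is that the measure is nominal by design. SAP 2.4.1 counts temporary interruptions as exposure, and protocol Table 6-2 leaves the Sandostatin LAR schedule to the physician, so other departures could be as large. That is true, and the 27-day convention should stay. It does not justify counting days after death, which are not exposure under any convention.

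Third, frequency is not shown. Entrants must be benefiting from treatment, and combination therapy ends with everolimus. This also stands: there may be no affected patient.

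Fourth, the repair may be incomplete. Protocol 7.1.5 describes the End of Treatment page as giving the date and reason for stopping, and protocol 8.1.1 keeps documented fatal progression out of serious adverse event reporting. A patient who stops for progression and dies soon afterwards may have no recorded death date. A footnote is needed for that case. It is no reason to leave known deaths uncorrected.

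Finally, the entries in SAP 5.1 and 5.1.1, which are marked as not applicable, concern imputation. They show only that no cap is placed there.

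**Conclusion.** The concern holds and is minor. As written, the four Sandostatin LAR and combination formulas credit max(0, 27 - d) days after death, which is an impossible value for an event the plan expects. The excess per patient follows from the formulas alone, given that the day of death counts as exposed and no everolimus dose is dated after death. The mean of 14.0 days, the percentages and the group-mean shifts rest on the assumed distribution of d, the assumed durations and the assumed n. The aggregate effect cannot be computed from the documents.

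**What to change.** In SAP 2.4.1, in the Sandostatin LAR days formula and both combination formulas, replace the last injection date plus 27 days with min(last injection date + 27 days, date of death). In the Sandostatin LAR years formula, make the same replacement for the last dosing date plus 27. Where a patient is known to have died but no death date is recorded, keep the uncapped value and footnote it.

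Optionally, if an exposure summary is run while patients are still on treatment (SAP 2.14 allows descriptive summaries of patients on drug), also cap at that analysis's own data cutoff. That cutoff is not 18-Mar-2016, which governs the RDC safety data.

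The cost is one sentence in the SAP and a minimum in the exposure program. No new data collection is needed: SAP 2.8.3 places death information on the End of Treatment page, and its on-treatment death table already needs the timing of death relative to last dose.
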